Targeting Worry to Improve Sleep

NCT03684057

June 5, 2019

Procedures:

Individuals will be recruited primarily via online advertising (e.g. Facebook and Google AdWords). Those who learn about the study via social media will be prompted to complete an online screening questionnaire. Those who learn about the study via other means (e.g. flyers, word of mouth) will review the questions from the online screener during the initial screening phone call. After the screening call, eligible participants will be scheduled for their baseline visit at the Brown Mindfulness Center ([name]). Study staff will send potential participants a copy of the consent form to review prior to the baseline visit. Participants will be asked to complete four study visits in total: three visits will be in-person and one will be completed online.

At the baseline visit, potential participants will be asked to review the consent form, ask any questions they may have about the study and if they decide to participate in the study, they will be asked to sign the consent form. Study participants will be given a copy of the signed consent form for their records.

Randomization Plan: A research team member who is not involved with the study will prepare sealed envelopes with an individual's group assignment using a block randomization scheme designed by an independent statistician. After the consent process and prior to administration of assessments, study participants will be randomized into one of two groups: 1) Group A – the treatment as usual group; 2) Group B - the UA intervention group. The participant will be given a sealed envelope and asked to open it to determine their group assignment.

Based on the participant's group assignment, the research team member will pull up the appropriate survey in Qualtrics and ask the participant to complete the first portion of the baseline assessment. After they have concluded, they will be instructed on how to complete the shape-matching task and then left alone to complete it on the study laptop while the researcher keeps track of the time from outside.

Upon completion of the assessments, the participant will be instructed to download either the Fitbit app (Group A) or Unwinding Anxiety and the Fitbit app (Group B). Please see below for onboarding specific to group assignment.

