If the participant is randomized to Group A - They will be given a Fitbit Inspire to track the quality of their sleep and asked to download the Fitbit app to their smartphone. They will be provided with the information necessary to set up their account and instructed how to use the app to track their sleep. Please refer to the included script, *Fitbit Setup Guide* attachment, for more details. They will be asked to wear the Fitbit and record what time they went to bed & woke up in a sleep diary (which will be provided) for one week after the baseline visit, one week before the 3rd visit (in-person), and one week before the 4th visit (in-person). The total number of hours slept per night will be collected for the post-baseline period in Qualtrics via a personalized survey link while data will be collected in person for the other two use periods and recorded in Qualtrics. Upon completion of the third assessment, the UA app will be downloaded to his/her smartphone at no cost and with lifetime access. The participant will be instructed to watch the first module of the app and will review its features with the research team member to ensure they do not have any questions (see *UA Setup Guide* attachment for more details).

If the participant is randomized to Group B - They will be given a Fitbit and the process outlined above will be followed. In addition, the UA app will be downloaded to his/her smartphone and the same process will be followed as outlined above.

Both groups are expected to complete the following tasks / assessments at each research visit:

Baseline – In-person

- Group A will complete the first eight items using a personalized survey link (based on participant ID) via Qualtrics

- Group B will complete the first seven items using a personalized survey link via Qualtrics and the seventh, the GAD-7, will be completed as part of the Unwinding Anxiety assessment.
- Both groups will complete the shape matching task on a study laptop.
 1. Demographics. This form will be filled out in Qualtrics (age, gender, socioeconomic status, employment, education, race/ethnicity, relationship status) (approximately 3 minutes)

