 9. Shape Matching Task. The shape matching task assesses cognitive control, or resistance to distraction. Individuals are presented with probe and target shapes and must decide whether they are the same shape. On some trials a distractor shape will be present, which the individual is instructed to ignore. (approximately 25 minutes)

Module 14 (Group B) or 1 Month (Group A) – Online

- Both groups will receive a personalized survey link via Qualtrics.

1. FFMQ non-reactivity (approximately 1 minute)
2. PSWQ (approximately 3 minutes)
3. MAIA (approximately 5 minutes)
4. PROMIS Sleep & Anxiety (approximately 1 minute)
5. WIS (approximately 1 minute)
6. GAD-7 (approximately 2 minutes)

Module 30 (Group B) or 2 Months (Group A)

- Group A will complete the first five items using a personalized survey link via Qualtrics and the sixth, the GAD-7, will be completed as part of the Unwinding Anxiety assessment.
- Group B will complete the first seven items using a personalized survey link via Qualtrics
- Both groups will complete the shape matching task on a study laptop.
 1. FFMQ non-reactivity (approximately 1 minute)
 2. PSWQ (approximately 3 minutes)
 3. MAIA (approximately 5 minutes)
 4. PROMIS Sleep & Anxiety (approximately 1 minute)
 5. WIS (approximately 1 minute)
 6. GAD-7 (approximately 2 minutes)
 7. Net promoter score (approximately 1 minute)
 8. Shape matching task (approximately 25 minutes)

2 Months post-intervention (Group B) or 4 Months (Group A)

- Both groups will complete the first six items using a personalized survey link via Qualtrics and the shape matching task will be completed on a study laptop.
 1. FFMQ non-reactivity (approximately 1 minute)
 2. PSWQ (approximately 3 minutes)
 3. MAIA (approximately 5 minutes)
 4. PROMIS Sleep & Anxiety (approximately 1 minute)

5. WIS (approximately 1 minute)
6. GAD-7 (approximately 2 minutes)
7. Shape matching task (approximately 25 minutes)

4. Participant Population.

Description of participant population:

We will recruit people who experience sleep disturbances related to anxiety in order to address Aims 1 & 2 of this study. We will recruit people who live within a 30-minute drive of Providence, RI because people who live within close proximity to Providence are more likely to return for follow-up visits and complete the study.

Participants will meet the following criteria:

Inclusion:

1. 18 years or older
2. PSWQ > 40 based on established cut-off suggesting GAD

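### The two arms complete the GAD-7 by different routes at baseline and, reversed, at the 2-month primary time point; use one route at every visit

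*Combined protocol and SAP*

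**What the plan says.** The Procedures section lists the questionnaires and their route visit by visit.

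- **Baseline.** "Group A will complete the first eight items using a personalized survey link (based on participant ID) via Qualtrics"; the GAD-7 is item 8 of that list. Group B does the first seven items in Qualtrics, "and the seventh, the GAD-7, will be completed as part of the Unwinding Anxiety assessment". Calling the GAD-7 the seventh item is a numbering slip that does not change the route.
- **Module 14 or 1 month.** "Both groups will receive a personalized survey link via Qualtrics".
- **Module 30 or 2 months.** For Group A, five items are in Qualtrics, "and the sixth, the GAD-7, will be completed as part of the Unwinding Anxiety assessment". In the other arm the GAD-7, here item 6, stays in the survey: "Group B will complete the first seven items using a personalized survey link via Qualtrics".
- **Last visit (2 months post-intervention or 4 months).** "Both groups will complete the first six items using a personalized survey link via Qualtrics", and the GAD-7 is again item 6.

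The Unwinding Anxiety assessment is not defined. On the order of events, the baseline text says "Upon completion of the assessments, the participant will be instructed to download either the Fitbit app (Group A) or Unwinding Anxiety", and the Group A onboarding text says "Upon completion of the third assessment, the UA app will be downloaded to his/her smartphone at no cost and with lifetime access".

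The Statistical Analysis Plan compares behavioral outcomes between arms at 2 months, which it calls the primary endpoint, by Welch's t-test (Mann-Whitney where normality fails). It also fits GEE models to change in each outcome at each follow-up.

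**The concern.** The GAD-7 moves to the Unwinding Anxiety assessment at exactly the visit where each arm receives the app: baseline for Group B, 2 months for Group A. How the score is obtained therefore depends on arm at the two visits that define the main contrast. Any effect of answering at app set-up rather than by survey link enters the estimated treatment effect. Because the routes swap between baseline and 2 months, the two shifts add in a change score instead of cancelling.

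A higher GAD-7 score means more anxiety. If the app route raises scores, Group B starts too high and Group A ends too high, so the app's benefit is exaggerated. If it lowers scores, a real benefit is partly hidden.

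The order of events adds a doubt. If the assessment sits inside the app, Group A's 2-month GAD-7, which should come from an unexposed control, may be answered during or after onboarding to the intervention.

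**Working it through.** **Routes, read from the Procedures**

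| Visit | Group A | Group B |
|---|---|---|
| Baseline | Qualtrics | Unwinding Anxiety assessment |
| 1 month / Module 14 | Qualtrics | Qualtrics |
| 2 months / Module 30 | Unwinding Anxiety assessment | Qualtrics |
| 4 months / 2 months post-intervention | Qualtrics | Qualtrics |

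**Bias.** Let a score by the Unwinding Anxiety route equal the true score plus m. With no true effect, the expected B minus A difference is:

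- 2-month score: 0 − m = −m
- change from baseline to 1 month: (0 − m) − (0 − 0) = −m
- change from baseline to 2 months: (0 − m) − (m − 0) = −2m
- change from baseline to 4 months: −m, by the same sum as at 1 month

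If the shift differs between the two visits, the 2-month change bias is the sum of the two shifts. If baseline GAD-7 enters the model as a covariate with slope b, the bias is (1 + b)m at 2 months and b·m at 1 and 4 months.

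**Inputs for scale.** The enrollment section gives 80 enrolled to obtain 64 usable data sets. Assuming 1:1 allocation, that is 40 or 32 per arm. The documents give no GAD-7 SD, no value of m and no correlation r between baseline and follow-up, so all three are assumptions. Tests are two-sided 5%, without multiplicity adjustment, using the noncentral t distribution.

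**Standard errors, in SD units, 32 per arm**

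- 2-month score: √(2/32) = 0.25
- change: √(2(1 − r)) × √(2/32), which is 0.25 at r = 0.5 and 0.194 at r = 0.7

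**Chance of a false positive, 32 per arm**

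| Contrast | m = 0 | m = 0.05 SD | m = 0.10 SD |
|---|---|---|---|
| 2-month score, Welch | 5.0% | 5.4% | 6.8% |
| 2-month change, r = 0.4 | 5.0% | 6.5% | 11.1% |
| 2-month change, r = 0.5 | 5.0% | 6.8% | 12.4% |
| 2-month change, r = 0.7 | 5.0% | 8.0% | 17.4% |
| 2-month, baseline as covariate, b = r = 0.5 | 5.0% | 6.3% | 10.5% |

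If the SD were 5 points, 0.05 and 0.10 SD would be 0.25 and 0.5 points. With 40 per arm and m = 0.10 SD the rates are 7.3% (Welch) and 14.3% (change, r = 0.5). With 32 per arm the error rate reaches 10% at m = 0.08 SD for the change contrast (r = 0.5) and at m = 0.17 SD for the Welch test. A simulation of 20,000 trials at m = 0.10 SD, r = 0.5 and 32 per arm agreed: mean differences were −0.100 for the 2-month score and −0.200 for the 2-month change, with rejection rates of 6.8% and 12.6%.

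**Can the trial's own data settle it?** The baseline difference between arms estimates m. With 40 per arm its SE is √(2/40) = 0.224 SD, so the 95% interval is about ±0.45 SD, and the chance of detecting m = 0.10 SD is 7%. It is also mixed with knowledge of allocation, because envelopes are opened before the assessments.

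**Half a fix.** Moving only Group A's 2-month form to Qualtrics leaves Group B's baseline shifted. The change contrast keeps a bias of m, and its error rate is 6.8% at m = 0.10 SD. With one route throughout, a constant shift cancels and both contrasts are unbiased.

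**The case against.** The main objection is that no shift has been shown. The items, response scale and self-report format are described once for both arms. The set-up guides and surveys are attachments that are not in the document. Read literally, the app is downloaded after the assessments are complete, so the Unwinding Anxiety assessment could be just another electronic form at the same in-person visit. That stands: m may be zero, and the error rates show only what a shift would do.

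The doubling needs equal shifts in newly randomized Group B participants and in Group A after two months' wait. Unequal shifts would add to something other than 2m, and shifts of opposite sign would partly cancel. This also stands. So does the point that adjusting for baseline GAD-7 would shrink the 1- and 4-month bias to b·m. The 4-month contrast is in any case no longer app against no app, because Group A has had the app since its third visit.

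The reach is limited. The PSWQ, WIS, PROMIS, MAIA and FFMQ items are in Qualtrics in both arms, the trial selects on PSWQ and WIS, and the GAD-7 is not named as primary. Raw GAD-7 scores at 1 and 4 months share a route, but neither visit is the primary time point. The planned False Discovery Rate correction would lower the error rates quoted here without removing the bias.

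These points limit the severity. They do not supply a reason for the arm-dependent route, and the difference cannot be repaired once the data are collected.

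**Conclusion.** The concern holds. The GAD-7 route differs by arm at baseline and is reversed at 2 months, and the plan neither states that the routes are equivalent nor adjusts for route. The bias is m in the 2-month comparison and, if the shift is the same at both visits, 2m in the 2-month change contrast. Its size is unknown and depends entirely on m, for which the documents offer no figure.

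This is a change that should be made rather than a fatal flaw. It concerns one outcome that is not named as primary, but that outcome is the battery's dedicated anxiety scale in a trial of an anxiety app. Confidence is medium, because the Unwinding Anxiety assessment is undefined and its place relative to the app download has to be inferred.

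**What to change.** Collect the trial GAD-7 through the Qualtrics link in both arms at every visit. Two cells change, Group B's baseline and Group A's 2-month GAD-7, and both must change. State in the Procedures that at these two visits every item, including the shape-matching task, is finished before the Unwinding Anxiety app is downloaded or viewed. If the app's own intake also asks the GAD-7, do not use those answers as the trial outcome.

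The cost is one block of about two minutes added to two existing surveys, plus one sentence on order. The other arm already answers the GAD-7 in Qualtrics at each of those visits. At worst, each participant answers the questionnaire twice at one visit. Visits, sample size and analysis are unchanged.

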 2. Five Facet Mindfulness Questionnaire (FFMQ) non-reactivity scale. The non-reactivity scale is a subscale of the 39-item FFMQ which is a self-report psychological measure of mindfulness skills. This subscale contains 7 items which are presented on a 6-point Likert scale ranging from 1 (almost always) to 6 (almost never). This questionnaire is included in the protocol. (approximately 1 minute)
 3. Penn State Worry Questionnaire (PSWQ). The PSWQ is a 16-item self-report measure of worry with items presented on a 5-point Likert scale ranging from 1 (not at all typical of me) to 5 (very typical of me). This questionnaire is included in the protocol. (approximately 3 minutes)
 4. Multidimensional Assessment of Interoceptive Awareness (MAIA). The MAIA is a 32-item self-report questionnaire comprised of 8 subscales including: noticing, not-distracting, not-worrying, attention regulation, emotional awareness, self-regulation, body listening, and trusting. Items are rated on a 6-point Likert scale ranging from 0 (never) to 5 (always). This questionnaire is included in the protocol. (approximately 5 minutes)
 5. PROMIS Sleep & Anxiety items. The PROMIS Sleep & Anxiety includes 5 questions taken from the PROMIS v1.0 Sleep Disturbance questionnaire which focus on the interaction between worry and sleep. This questionnaire is included in the protocol. (approximately 1 minute)
 6. Worry Interfering with Sleep scale (WIS). The WIS is a single item self-report question that asks individuals to rate what percent of time worry interfered with their ability to get to or stay asleep. This questionnaire is included in the protocol. (approximately 1 minute).
 7. Expectancy. These three questions assess treatment usefulness, confidence, and likelihood to recommend on a 9-point Likert scale from 1 (Not at all confident or Not at all useful) to 9 (Very confident or Very useful) and from 0 to 100%. This questionnaire is included in the protocol (approximately 1 minute).
 8. Generalized Anxiety Disorder 7-items (GAD-7). The GAD-7 is a 7-item measure of anxiety rated on a 4-point Likert scale ranging from 0 (Not at all sure) to 3 (Nearly every day). This questionnaire is included in the protocol. (approximately 2 minutes)

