3. $\geq 5/10$ on Worry Interfering with Sleep scale (WIS)
4. Able to read and speak English, because the Unwinding Anxiety app is available in English only.
5. Owns a smartphone (UA app can only be used on a smartphone)
6. Willingness to wear the Fitbit Inspire tracker

Exclusion:

1. If using psychotropic medication - not on a stable dosage for at least 6 weeks
2. Medical disorder of the severity that would interfere with ability to participate (e.g. cancer, multiple sclerosis, Parkinson's disease, ALS, etc. These disorders impact sleep quality which could confound study outcomes.)
3. As needed (i.e. prn) benzodiazepine or hypnotic sleep aid
4. Known sleep disorder (e.g. obstructive sleep apnea, restless leg syndrome – because these disorders impact sleep quality.)
5. Psychotic disorder (Mindfulness meditation has to be carefully monitored with people experiencing psychosis. We are not able to provide this type of monitoring given budget constraints.)
6. Post-Traumatic Stress Disorder (Mindfulness meditation has to be carefully monitored with people experiencing PTSD. We are not able to provide this type of monitoring given budget constraints.)
7. Severe Depression (PHQ-2 score > 3) (People experiencing severe depression may also experience sleep disorders which could confound study outcomes.)
8. Current shift work employment (People working alternate shifts may have sleep quality problems which could confound study outcomes.)
9. BMI > 30. (People who are obese may have sleep quality problems which could confound study outcomes.)
10. Evening caffeine use (Caffeine use late in the day can impact the quality of a person's sleep, hence the possibility of confounding study outcomes.)
11. Pregnancy (Women in various stages of pregnancy often have sleep quality problems, hence the possibility of confounding study outcomes.)
12. New parents whose child is not sleeping through the night (New parents are often awakened every 3 – 4 hours by a newborn which could confound study outcomes)
13. Lives in same household as someone already enrolled in this study (To prevent study participants from sharing study information with one another.)

Participant enrollment target:

Our goal is to collect 64 complete and usable data sets, so our plan is recruit and enroll 80 participants.

Enrolling 80 participants will be sufficient to cover any participants who don't complete the study and it will allow us to meet our N of 64.

Check-ins

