The Project Coordinator will check in with participants regarding their experience with the app at 7, 14, and 45 days after they receive access. The purpose of these calls is to encourage engagement with the app in addition to providing a time for the participant to address any questions, comments, likes/dislikes with the Project Coordinator. These will be done via the participants preferred contact method (phone call or text message) and the Project Coordinator will establish preferred times at the baseline assessment. In the event that the Project Coordinator cannot reach the participant, an additional outreach attempt will be made within 24 hours. If this is unsuccessful, no additional contact will be made until the next check-in point. If two consecutive check-ins are missed, an additional email will be sent. Responses may be recorded in Qualtrics and coded solely by participant ID to ensure confidentiality.

5. Recruitment Methods

We will recruit residents who live within a 30-minute drive of Providence, RI primarily using social media advertising (e.g. Facebook, Google AdWords), flyers and info cards, and the Brown Mindfulness Center website.

Social Media

Web page advertisement that briefly describes the study and link to a landing site where potential participants can complete the PSWQ and WIS to determine their eligibility and submit their name, phone number, and email address if interested (see *Landing Page* and *Online Screener* attachments for more details). The contact information will be transferred securely using Stronghold by our Brown-approved consultant, [name] (PSA is already in place). Please see *Social Media Ad* attachment for more details.

Flyers

Physical copies of the flyer will be posted on bulletin boards, in waiting rooms, etc. Digital copies will be provided upon request for use on Facebook, websites, and listservs. Please see *Flyer* attachment for more details.

- Brown University campus and surrounding areas
- RISD campus and surrounding areas
- Cafes, grocery stores (e.g. Whole Foods), community boards

Website

Information about the study will be provided on the Brown Mindfulness Center website along with a link to the landing site where potential participants can determine their eligibility. Please see *MC@B Website Ad* attachment for more details.

Brown Mindfulness Center

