Information about the study will be on display at the Brown Mindfulness Center. This will be a smaller version of the flyer that is easy for individuals to take with them.

Procedure for all recruitment channels

Both the Project Coordinator and Project Director (both CITI/GCP certified) will be responsible for screening potential participants on the phone. This section is denoted in brackets and underlined and does not refer to one individual specifically.

Potential participants enter the screening pipeline either by reaching out to the Project Coordinator directly or by completing the online initial screening questions.

Online screening questions –

Contact information (name, email, and phone number) will only be collected from participants who are deemed eligible by the online screener using survey logic (e.g. PSWQ > 40 and \geq 5/10 on WIS). This will be collected and retained in Qualtrics and only accessed by the Project Coordinator. If an individual is eligible, their contact information will be entered into the key code stored in Stronghold and the study record in Qualtrics will be deleted upon the participant agreeing to participate in the study. If the individual is not eligible after the phone screen, their information will be deleted immediately.

Participants who completed the online screening questions –

Individuals will be screened for eligibility over the phone. The research team member will first describe the study and ask if the individual is interested in moving forward with the screening process. Upon determination of eligibility based on the inclusion/exclusion criteria, the person will be asked again if they wish to participate (see *Phone Screening – Online Screener* attachment for more details). If they are interested in moving forward with the study, the baseline assessment will be scheduled and a copy of the main consent form and directions to the Mindfulness Center at Brown University will be emailed to them (see *MC@B Directions* and *Baseline Scheduling Confirmation Email* attachments).] The online screener should take no more than 5 minutes and the screening call should take no more than 10 minutes.

Participants who did not complete the online screening questions –

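### No criterion excludes, and no listed form records, prior or current use of the Unwinding Anxiety app; the likely effect is a small dilution of the contrast in both arms

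*Combined protocol and SAP*

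**What the plan says.** **Recruitment.** Procedures describes online advertising as the main source. Section 5 (Recruitment Methods) gives the channels as "primarily using social media advertising (e.g. Facebook, Google AdWords), flyers and info cards, and the Brown Mindfulness Center website". On the website: "Information about the study will be provided on the Brown Mindfulness Center website along with a link to the landing site". On the premises: "Information about the study will be on display at the Brown Mindfulness Center", as a small flyer to take away.

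**Eligibility.** Section 4 (Participant Population) lists 6 inclusion and 13 exclusion criteria. Mindfulness appears among them only as the safety reason for excluding psychotic disorder and PTSD. The one criterion aimed at contamination is exclusion 13: "Lives in same household as someone already enrolled in this study (To prevent study participants from sharing study information with one another". It covers contact between enrolled members of one household and nothing else. Inclusion 4 requires English "because the Unwinding Anxiety app is available in English only", so the app is treated as an existing product.

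**Screening.** For the online route, "Contact information (name, email, and phone number) will only be collected from participants who are deemed eligible by the online screener using survey logic"; the examples of that logic are the PSWQ and WIS cut-offs. For the phone screen, "Upon determination of eligibility based on the inclusion/exclusion criteria, the person will be asked again if they wish to participate".

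**Data and analysis.** The demographics form covers age, gender, socioeconomic status, employment, education, race/ethnicity and relationship status. Group A is treatment as usual and receives the app after the third assessment (2 months). The Statistical Analysis Plan sets 2 months as the primary endpoint, uses an intent-to-treat approach, and adds a per-protocol analysis that it does not define.

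**The concern.** The exclusion list removes several influences on sleep, such as evening caffeine, shift work and BMI above 30, on the ground that they could confound the outcomes. Prior exposure to the tested intervention bears more directly on the treatment contrast than any of these, and it is not on the list.

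A current user of the app assigned to Group A would be a control who already has the intervention. The same person assigned to Group B would be given something they already have. In either arm they may contribute little to the difference at 2 months. The mindfulness outcome could be affected too, since "The non-reactivity scale is a subscale of the 39-item FFMQ which is a self-report psychological measure of mindfulness skills", and an existing user may start with a raised score.

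Nothing later in the plan would reveal this. If use is never recorded, the SAP's confounder adjustment cannot include it, the per-protocol analysis cannot act on it, and a null result could not be separated from a diluted comparison.

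**Working it through.** **1. Is the gap there?** Set side by side:

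| Place | Covers prior or current UA use? |
|---|---|
| 6 inclusion criteria | No |
| 13 exclusion criteria | No; number 13 covers shared households only |
| Online screener logic, as described | PSWQ and WIS given as examples; no exposure item mentioned |
| Phone screen | Follows the listed criteria |
| Baseline demographics form | No |
| SAP | No adjustment or sensitivity analysis for it |

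The gap is in every part of the plan that can be read.

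**2. The plan's own figure.** The only sample-size figures are 80 enrolled and 64 complete data sets. The implied loss is 1 − 64/80 = 20%, and 64/(1 − 0.20) = 80, so the enrollment target reproduces. The 64 itself cannot be reproduced, because no effect size, SD, alpha or power is given.

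**3. How much could it matter?** Inputs:

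- From the document: 64 completers.
- Assumed: equal allocation (32 per arm), two-sided alpha 0.05, a true standardised effect d of 0.7 (0.5 as an alternative), an unchanged SD, the same exposed fraction f in both arms, and no between-arm difference among exposed people. The last is a worst case.

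The diluted effect is d × (1 − f). The two-sample t-test has 62 degrees of freedom, critical value 2.00 and noncentrality d(1 − f) × √(32/2) = 4d(1 − f).

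| f | People among 80 | Effect (d = 0.7) | Noncentrality | Power (d = 0.7) | Power (d = 0.5) |
|---|---|---|---|---|---|
| 0 | 0 | 0.700 | 2.80 | 78.7% | 50.4% |
| 2.5% | 2 | 0.683 | 2.73 | 76.7% | 48.4% |
| 5% | 4 | 0.665 | 2.66 | 74.5% | 46.4% |
| 10% | 8 | 0.630 | 2.52 | 69.9% | 42.6% |

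**4. A milder assumption.** If exposed people keep half the effect, the multiplier is 1 − f/2. At f = 10% and d = 0.7 the effect is 0.7 × 0.95 = 0.665 and power is 74.5%, the same as the 5% row.

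**5. Which rows are plausible?** The document gives no figure for the share of recruits from the center or for prior use of the app. Online advertising is the main source and the criterion at issue concerns one specific app, so the 2.5% and 5% rows (2 to 4 people of 80) seem more realistic than 10%. That is a judgement, not a figure from the plan.

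**The case against.** **Randomisation protects the comparison.** A reader might infer that Group A in particular is contaminated and the result biased. The document does not support that. Assignment is block-randomised, so prior users fall in both arms in expectation. Chance imbalance is possible, but the standard error already reflects it. What remains is dilution.

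**Past mindfulness training is not the same as being treated.** A reader might extend the point to graduates of mindfulness courses and call for their exclusion. Nothing in the document shows that such people gain nothing from UA. Everyone enrolled must have PSWQ above 40 and WIS of at least 5/10, so they still have room to improve. The comparator is treatment as usual, stable psychotropic medication is allowed, and no criterion bars ongoing psychotherapy. Leaving mindfulness experience unrestricted is consistent with that design, and excluding it would narrow the population for a debatable gain. This objection stands, and the point is limited to the app.

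**Large losses of power are speculative.** Exposed fractions of 10% to 20% with zero effect would mean 8 to 16 of 80 participants. That does not sit with expecting to lose only a few recruits by excluding them. This stands too.

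**Some material cannot be seen.** The screener and both phone scripts are attachments, and the online logic is introduced only by example. A script might ask about prior use. But eligibility is said to follow the listed criteria, so such a question would have no criterion to act on.

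**Baseline adjustment helps.** FFMQ non-reactivity is measured at baseline, and the GEE analyses model change with adjustment for confounders. This partly absorbs differences in starting level. It does not undo dilution, and FFMQ is only an indirect sign of prior app use.

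**Conclusion.** The point holds in a narrow form. A prior or current user of the tested app is eligible for either arm, and the visible plan would not record it. The consequence is dilution toward no difference, not a systematic bias in Group A.

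The loss is probably small: about 2 to 4 percentage points of power if 2.5% to 5% of participants are exposed, and about 9 points at 10%. These figures rest on assumptions not in the document: 32 completers per arm, two-sided 0.05, d = 0.7 and no effect among exposed people. The true fraction is unknown. That the app can be obtained outside the study is inferred from the wording of inclusion 4 and from its being supplied to participants free of charge; the document does not say so outright. Severity: minor, worth correcting because it is cheap.

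**What to change.** 1. Add an exclusion for prior or current use of the Unwinding Anxiety app, with one matching question in each of the two phone-screening scripts.
2. At baseline, record prior and current participation in mindfulness programmes in both arms. Do not exclude on it; pre-specify a sensitivity analysis that uses it.
3. At the 2-month visit, before the app is installed, ask Group A whether they used UA in the meantime. Use the answer only in the planned per-protocol analysis, and state there how it defines that set. Leave the intent-to-treat analysis unchanged, since this is information from after randomisation.

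**Cost.** One criterion, one screening question, and one or two added questions at existing visits. A few recruits may be lost, mainly from the mindfulness-center channel; with online advertising as the main source this should be easy to replace.
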